5.1 Recruitment plan and consent of participants

At each participating site, the local research team will meet with the obstetrical team to identify potential candidates for participation in the study. Following that, eligible patients will be approached early in their labor stage to assess willingness to participate. If consent is obtained, the research team members will follow the course of the delivery. At the time of birth, infants will only be included if ≥ 35 weeks of gestational age and clinically stable as determined by the attending pediatrician. Written consent will be obtained from parents prior to enrollment. The study protocol has been designed respecting the special moment around birth. Hence, parents will be approached and receive explanation about the study design before delivery and given ample time to make an informed decision. Families will be able to withdraw from the Study at any time. However, any data collected up to date of withdrawal will not be destroyed in order to maintain the integrity of the study design. No further data will be collected once a participant is withdrawn from the Study.

As the study is not a randomized clinical trial a Data Safety and Monitoring Committee (DSMC) will not be established. However, interim evaluations for safety will be done by the lead site after 200 and 400 patients have been studied to review data related to safety, including skin lesion, pain scores, and HCPs survey responses. Any adverse event or evidence of discomfort during monitoring, including placement and removal of sensors (expected to be negligible) will be recorded and reported to the local investigator and the Principal Investigator at the lead site.

Recruitment material in the form of posters and brochures will be provided to all the sites explaining the Study and how to get additional information if interested.

5.2 Regulatory and Legal Considerations

The Sponsor-Investigator [name] will lead this multicenter prospective study at the lead site with co- investigators [name] and [name] PhD. As Principal Investigator/Sponsor-Investigator [name] responsibilities include all aspects of study design, education and training on the study, study conduct, data analysis, student supervision, and preparation of the data for presentation and publication, regulatory oversight and overall responsibility for the conduct of the study at all participating sites. The lead site Principal Investigator is responsible for ensuring the study is conducted according to professional standards relating to the proper conduct of research such as ICH-Good Clinical Practice guidelines and Health Canada regulations and ISO guidelines for Class II device studies. The lead site Study personnel will provide support with regulatory and research ethics board approvals at the participating sites, as well as comprehensive training on the protocol, monitoring systems, data collection and data management.

The participating Site Investigator(s) will be responsible for ensuring the proper conduct of the study at their center, accurate data collection and management, and timely transfer of data to the lead site. They will also present the study to their faculty, their NICU personnel, their Obstetric division personnel, and help facilitate communication between sites.

With the support and expertise of the RI-MUHC Capture and Optimization of Research Data (CORD) Unit, data collection, management, and a REDCap study database will be set up at the RI-MUHC. Input from the participating sites will ensure a comprehensive, secure, and user-friendly data capture and analysis strategy is implemented for all study sites. The CORD platform and the Principal Investigator entered into a service agreement for the cost of the CORD services and support.

Prior to initiating the Study at participating sites, the RI-MUHC and Principal Investigator will enter into inter-institutional research collaboration agreements with each participating site. These site agreements will establish the responsibilities of both the lead site and the participating sites. The agreement will include the budget for each participating site and collaboration terms. The agreements will ensure data shared with the lead site is in accordance with applicable legal frameworks for the security, privacy, and confidentiality of the health information of the study participants. These agreements will also ensure that the participating sites comply with all regulatory guidelines, standard operating procedures, and the requirements of their particular countries and institutions, including obtaining REB and local regulatory approvals before initiating the study at their respective institutions.

The protocol will be made publicly available at clinicaltrials.gov before initiation of the study at the lead site. Informed consents have been prepared by the lead site Study team and will be shared with the participating sites and translated to their respective languages.

Principal Investigator as Sponsor will retain all source documents and study related documents for 15 years as required by Health Canada. Sponsor will maintain the right to monitor and audit participating sites as required by ICH-GCP including access to all study related essential documents including source documents.

6 Publication Policy

It is expected that this research study will result in one or more multi-center publications. The Principal Investigator retains the right to publish the results independently and at his discretion. No site can publish any publication, including but not limited to a publication in the form of a presentation, abstract, protocol, poster or manuscript without the consent of the Principal Investigator. However, once the study is complete and the first multicenter manuscript is published sites may publish results of their site study data independently. All publications and presentations by any site must be sent to the Principal Investigator, who maintains the ability to comment and request confidential information to be removed, prior to submitting for publication. All site publications must acknowledge the Smart Hospital Project, authorship will be according to ICMJE guidelines and all publications will acknowledge the funding support as follows:

1. PATIENT INFORMATION

Patient ID (code)*	Sex	Type of delivery	Gestational age (at birth)	Time of birth (HH:MM)	Birth weight (grams)	APGAR score (1, 5 and 10')	Munsell Scale Score
R-_____	 M  F	 Vaginal  C-section	____ weeks ____ days				

2. PAIN ASSESSMENT

Score:

Facial Expression	
0 – Relaxed muscles	Restful face, neutral expression
1 – Grimace	Tight facial muscles, furrowed brow, chin, jaw, (negative facial expression – nose, mouth, brow)
Cry	
0 – No cry	Quiet, not crying
1 - Whimper	Mild moaning, intermittent
2 – Vigorous Cry	Loud scream; rising, shrill, continuous (Note: silent cry may be scored if baby is intubated as evidenced by obvious mouth and facial movement.)
Breathing Patterns	
0 – Relaxed	Usual pattern for this infant
1 – Change in Breathing	Indrawing, irregular, faster than usual, gagging, breath holding
Arms	
0 – Relaxed/Restrained	No muscular rigidity, occasional random movements of arms
1 – Flexed/Extended	Tense, straight legs; rigid and/or rapid extension/flexion
Legs	
0 – Relaxed/Restrained	No muscular rigidity, occasional random movements of legs
1 – Flexed/Extended	Tense, straight legs; rigid and/or rapid extension/flexion

State of Arousal	
0 – Sleeping/Awake	Quiet, peaceful, sleeping, or alert random leg movement
1 – Fussy	Alert, restless, thrashing
TOTAL	

***R**=Royal Victoria Hospital; **U** = UNICAMP; **B** = Uberlandia; **S** = Sanatorio Trinidad Palermo Hospital; **M** = Mbuya Nehanda Hospital (Harare, Zimbabwe); **N** = Neocare Baby Hospital (Harare, Zimbabwe); **C** = Maputo Central Hospital (Mozambique); **T** = Hospital Sanatorio Trinidad Palermo; **V** = Hospital Ramos Mejía; **H** = Hospital of Newborn Medicine (Buenos Aires, Argentina)

3. MONITORING INFORMATION

Order of monitoring (w = wired, s = wireless) ; i.e. 1w,2s	
Placement of limb wired sensor, if applicable (RA = right arm, LA = left arm, RL = right leg, LL = left leg)	
Placement of vital signs wired sensors, if applicable (C = chest, B = back)	
Number of wired leads	
Placement of limb wireless sensor, if applicable (RA = right arm, LA = left arm, RL = right leg, LL = left leg)	
Placement of vital signs wireless sensors, if applicable (C = chest, B = back)	
Operator/nurse responsible for placement of monitors	

4. VITAL SIGNS MONITORING LOG

		0 (Baseline)	15	30	45	60	75	90	105	120
Time										
Heart rate (bpm)	Wired									
	Wireless									
Respiratory rate	Wired									
	Wireless									

(breaths per minute)										
Oxygen saturation (SpO2)	Wired									
	Wireless									
Axillary temperature (°C)										
Newborn Location (k = kangaroo care, c = in bed, ma = mother arms, fa = father arms, o = other, specify)										
Newborn Position (s = supine, p = prone, side line =sl, o = other, specify)										

5. COMMENTS LOG

Comments	0 (Baseline)	1	2	3	4	5	6	7	8
Time wired Monitor									
Time wireless Monitor									
Location of newborn (k = kangaroo care, b = in bed)									
Time (clock)									
Position of newborn (s = supine, p = prone, side line =sl)									
Time (clock)									

Muscle tone (normal = n, hypotonic = hypo, hypertonic = hyper)								
Time (clock)								
Quality of reading (N/A = no issue, A = presence of artifact, P = poor signal capture)								
Time (clock)								
Interventions performed during recording (N/intervention)								
Time (clock)								
Sensor disconnection (N/reason*)								

6. COMMENTS LOG – CODE WORDS (for redcap)

Event	Drop-Down Code	Details
Kangaroo Care = KC	KC start	Start of kangaroo care
	KC end	End of kangaroo care
Nursing Care = NC	NC check	Quick nurse check (may open incubator, no real manipulation of infant)
	NC start	Routine care, that is longer than quick check, includes diaper change, feeding, etc)
	NC end	End of routine care procedures
Parent Care = PC	PC start	Holding baby, changing diaper, umbilicus care, bath time
	PC end	End of parent care procedures
Breastfeeding = BF	BF start	Start of breastfeeding
	BF end	End of breastfeeding
Repositioning = R	R supine	Baby repositioned to supine
	R prone	Baby repositioned to prone
	R Side	Baby repositioned to side
	E end	Exam end

xEvent Other	EO [specify]	Other relevant event not accounted for by annotations list please specify
Sensors (both) = S	SR start	Sensors removed for
	SR end	Sensors placed back
Chest Sensor = C	CR start	Chest sensor removed for exam
	CR end	Exam over chest sensor placed back on
	CA	Chest sensor readjustment
Limb Sensor = L	LR start	Limb sensor removed
	LR end	Limb sensor back on
	LA	Limb sensor readjustment
	LX	Limb sensor falling off [ES1]
	LH right	Limb location change – now on right hand
	LH left	Limb location change – now on left hand
	LF right	Limb location change – now on right foot
	LF left	Limb location change – now on left foot
Drager Electrodes = E	ER start	Electrodes removed
	ER end	Electrodes back on
	EA	Electrodes readjusted/moved
Massimo Oximeter = O	OR start	Oximeter removed
	OR end	Oximeter back on
	OA	Oximeter readjusted
	OH	Oximeter moved to hand
	OF	Oximeter moved to foot
Temperature and Humidity	T() H()	Temperature and humidity recording

7. ADDITIONAL OBSTETRICAL INFORMATION

Maternal age	
Gesta / Para / Abortion (G/P/A)	
Medications during pregnancy	
Medications during delivery	
Pre-eclampsia	
Diabetes	
Infection	
Use of forceps during delivery (Y/N)	
Use of vacuum extraction (Y/N)	

8. ADVERSE EVENTS RELATED TO MONITORING

WIRED SENSORS

- None
- Skin irritation: () Chest or () Limb
- Skin erosions: () Chest or () Limb
- Skin bleeding: () Chest or () Limb

Skin photos: Chest Limb

Neonatal Skin Condition Score (NSCS)*
Chest: Limb:

WIRELESS SENSORS

- None
- Skin irritation: () Chest or () Limb
- Skin erosions: () Chest or () Limb
- Skin bleeding: () Chest or () Limb

Skin photos: Chest Limb

Neonatal Skin Condition Score (NSCS)*
Chest: Limb:

Treatment required: Yes: () No

Chest Neonatal Skin Condition Score (NSCS)* will be done by a blinded dermatologist at the end of the AWARD project.

Signature of data collector: _____

Date (YYYYMMDD): _____

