2.2 Aims

Healthcare technology assessment is the multidisciplinary evaluation of medical technologies with regard to **feasibility, safety, efficacy**, indications for use, cost, and cost-effectiveness. A complete assessment should explore the scientific, ethical, economic, and social reasons for adopting a technology and it may influence the quality of service and distribution of resources.

In this multicenter study, we aim to assess the first 3 important criteria.

Aim 1 – To determine the **feasibility** of using a wireless system immediately after delivery and for the first 2h of age, while in the obstetrical center under unsupervised parents' care. The following outcomes will be measured for both wired and wireless systems:

- a. Percentage of time for which HR, RR, SpO₂ and T_{skin} data are displayed.
- b. Occurrence of gaps in signal detection/recordings (% and length).
- c. Causes of the gaps in signal detection/recordings.
- d. Descriptive analysis of user surveys and their satisfaction with the wireless system.

Aim 2 - To investigate the **safety** of using this wireless system immediately after delivery and for the first 2h of age. The following outcomes will be measured for both wired and wireless systems:

- a. Skin score to be determined by a blinded dermatologist using de-identified pictures of the skin after removal of the sensors of each system.
- b. Pain scale to assess any discomfort or pain during the removal of the sensors.
- c. Clinically significant events detected by the wired system (HR < 100 bpm or SpO₂ < 80%) but missed by the wireless system.

Aim 3 – To assess the **accuracy** of this wireless system in measuring HR, RR, SpO₂ and T_{skin} signals compared with the “standard of care” wired system. The following outcomes will be computed:

- a. Correlation coefficient
- b. Slope
- c. Variance accounted for
- d. Bias

Further subgroup analyses will be conducted to assess for systematic differences in feasibility, safety, and accuracy of the wireless system between the following:

- High vs. Low and Middle income countries
- Female vs. Male subjects
- Term vs. Preterm (born < 37 weeks gestational age) infants
- C-section vs. Vaginal delivery

- Skin pigmentation

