3.3.4 Data Collection

The Study research team at each site will collect standard demographic and clinical information from mothers and newborns as described in the Data Collection Form (see Appendix 1) during the 2hrs of vital sign recording (see Figure 11 below). With a stopwatch, a designated trained research team member(s) will time the recording as the period (sec.) that elapses from the application of the leads until the first display of data on the monitors, for all the sensors of both systems. Data will be continuously recorded while the mother/caregiver provides routine care. Annotations as described in the Data Collection Form will be documented by the research team regarding movements, breast-feeding attempts, cleaning/drying, patting, etc. (see Appendix 1). The vital signs data displayed on the monitors will only be visible to designated research team member(s), and all alarms will be turned off so as not to disturb parents and newborn. Any clinically relevant changes observed in vital sign parameters will be communicated by the research team member(s) to the obstetrical/neonatal team. A clinically relevant event is defined as follows: HR < 100 bpm or SpO₂ <85% (after the first 10 minutes of life) with sinusoidal wave as detected on either monitoring system during the course of the 2hr continuous monitoring. If the neonate requires any intervention to reverse instability, such as oxygen therapy and ventilator support, data collection will end but the data collected up to that time point will be included. The participating baby will not be withdrawn from the study.

The following data will be collected:

- Skin assessment:* In order to assess the safety of the wireless skin sensors, photographs of the infant's skin will be taken before device placement and after device removal. Each participating site will send de-identified digital photos coded (with the participant's study code) to the dermatologist for blinded assessment using the skin score (Neonatal Skin Condition Score - NSCS) as described in the Data Collection Form.
 - **Neonatal Skin Condition Score (NSCS)³⁷:** Photographs of the infant's skin at the site of device placement for both the chest and limb skin sensors will be taken prior to device

placement and following device removal. These photographs will then be scored by a dermatologist using the NSCS. Scores range from 3 (intact skin condition) to 9 (very poor skin condition).

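### The blinded skin score (Aim 2a) is dated to the end of the project, so no blinded skin scores will exist at the safety reviews after 200 and 400 infants

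*Combined protocol and SAP*

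**What the plan says.** Section 2.2 lists the first safety outcome, Aim 2a, as "Skin score to be determined by a blinded dermatologist using de-identified pictures of the skin after removal of the sensors", measured for both systems. Section 3.3.4 gives the procedure. The skin is photographed at the chest and limb positions before placement and again after removal, and sites send coded images "to the dermatologist for blinded assessment using the skin score". It adds: "These photographs will then be scored by a dermatologist using the NSCS". It gives no date for the reading.

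The date appears only in Appendix 1, section 8, where a line about the NSCS says that it "will be done by a blinded dermatologist at the end of the AWARD project". The same section of the form has bedside adverse-event boxes for each system, such as "Skin irritation: () Chest or () Limb", with matching boxes for erosions and bleeding and an entry for whether treatment was required. A data collector signs the form.

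Section 5.1 states that "a Data Safety and Monitoring Committee (DSMC) will not be established". It then says that "interim evaluations for safety will be done by the lead site after 200 and 400 patients have been studied", to review safety data "including skin lesion, pain scores, and HCPs survey responses". It also requires adverse events and signs of discomfort to be recorded and reported to the local investigator and to the lead-site investigator.

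**The concern.** The interim reviews are what section 5.1 offers after ruling out a committee, and the plan names no other aggregate look at safety. Skin effects are an obvious risk of an adhesive sensor on a newborn. Section 1.3 says that the chest sensor was modified after the phase 1a study and that the type of adhesive was among the changes, so earlier skin experience may not carry over directly.

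If the outcome chosen to judge skin safety is read only at the end, neither review can use it. A skin effect that a blinded reader would grade, but that bedside staff did not tick, might not show in the aggregate data until every infant had been monitored.

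**Working it through.** The plan gives no figure to reproduce here. The check is mainly one of timing.

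**Inputs**
- Planned total: 600 infants, 100 at each of 6 sites (section 4).
- Reviews: after 200 and after 400 infants (section 5.1).
- Blinded NSCS: end of the project (Appendix 1, section 8). No other section gives a date or schedules an interim reading.

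**Step 1: where the reviews fall.** 200/600 = 33.3% and 400/600 = 66.7% of planned enrolment. Both come before the end of the project.

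**Step 2: blinded scores available.** 0 of 200 at the first review and 0 of 400 at the second.

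**Step 3: infants still to come.** 600 − 200 = 400 after the first review and 600 − 400 = 200 after the second. Section 5.1 does not say that enrolment pauses for a review, so these are upper figures.

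**Step 4: what skin information the reviews would have.**
- *Bedside boxes* (irritation, erosions, bleeding, treatment required). They are available. They are not described as blinded, the form gives no definitions or grades, and there is no pre-placement entry.
- *Individual adverse-event reports.* They are available, but they too depend on someone at the bedside recognising a problem.
- *Photographs.* They are uploaded to REDCap and the study Dropbox (sections 3.3.4 and 3.3.5), and the lead site can reach the full database. They are available but unscored, and the plan does not say that the reviews will look at them.
- *Health-professional survey* (Appendix 2). It is on the interim list, but its item on skin lesions and pressure sores (question 5) asks about the standard wired system. For the wireless sensors, questions 11 and 12 offer only a general safety option.

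**Step 5: what timely reading could show (illustration only).** Take the proportion of infants with a raised score on one system, with exact (Clopper-Pearson) two-sided 95% limits.
- 0 of 200: upper limit = 1 − 0.025^(1/200) = 1.8%.
- 10 of 200: 5.0%, with limits 2.4% to 9.0%.

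The count of 10 is invented to show the precision at the first review. No document gives an expected rate, and section 5.1 states no skin threshold against which either result would be judged.

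**The case against.** The case for leaving the plan as it is has several parts.

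- **There is no contradiction.** Section 5.1 promises a review of skin lesions and does not name the NSCS. The form's boxes can supply that item by system and by chest or limb. This stands.
- **Other safeguards exist.** A reader might infer that the two reviews are the only protection against skin injury, or that the tick boxes are the only skin data. The documents support neither. Section 5.1 also requires adverse events to be reported infant by infant, the form records treatment, and the lead site holds the photographs. What is missing is the blinded score.
- **Under-reporting by a site could be noticed.** A reader might infer that it could not be. Sites send completed forms monthly for query, and the photographs are there to compare. No cross-check of forms against photographs is planned, however, so this cover is possible but not assured.
- **The NSCS is not shown to be the better detector.** Appendix 3 grades erythema by share of body surface and has no bleeding item. This stands, and it is a reason to use the score beside the bedside entries and not in their place. What the score adds is a blinded reading with a pre-placement photograph for comparison.
- **One reading at the end favours consistent scoring.** This is a legitimate aim, and it is the one real cost of reading in batches.
- **The text is thin.** The timing rests on one line of a form, and as printed that line opens with the word Chest. The asterisk in it also marks the NSCS heading over both chest and limb for each system, and nothing gives an earlier date for the limb score. Reading it as covering both is the more natural sense.

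**Conclusion.** The point holds as a gap between the plan's skin safety outcome and the data its interim reviews will have. Followed as written, the plan gives blinded scores for 0 of 200 and 0 of 400 infants at the two reviews, with up to 400 and 200 infants still to be monitored. This rests on two readings: that the form's timing line covers both chest and limb, and that the end of the project falls after the 400th infant.

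The point does not reach further. A reader might infer that the Aim 2a result itself is compromised, but the final estimate uses the same photographs and the same reader whenever they are read. Nor do the documents show that the bedside route would miss injuries. They show only that the reviews would lack the blinded outcome. The change is a worthwhile, inexpensive improvement and not an essential correction.

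**What to change.** In Appendix 1, section 8, replace the end-of-project timing with batch reading by the same blinded dermatologist, naming both chest and limb: photographs from infants 1–200 before the first review, 201–400 before the second, and the remainder at the end. Give the same schedule in section 3.3.4, which is now silent on timing.

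In section 5.1, state that the interim skin review uses these scores by system and sensor position, beside the bedside adverse-event entries.

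The cost is a wording change in three places. The reader and the number of photographs stay the same, apart from a few repeat readings, and the images are already uploaded centrally. The downside is possible drift in scoring between batches. Including a few earlier photographs in each later batch lets this be checked and reported.
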